#### **Well-being (WHO-5)**

To measure the extent of well-being we will administer the WHO-5 Well-Being Index (WHO-5). The WHO-5 is one of the most widely used questionnaires assessing well-being and consists of five simple, non-invasive questions (14). The five items are assessed on a 6-point Likert scale ranging from 0 to 5 and the individual item scores are added together and transformed into a 100 point scale with lower scores indicating worse well-being. The WHO-5 has been found to correlate moderately to strongly with diabetes specific measures of distress and depression in both T1DM and T2DM (15, 16).

#### **Stress: PSS**

*Perceived Stress Scale (PSS)*: The PSS is a 10 item scale designed to measure the degree to which situations' in one's life are appraised as stressful (17). Participants rate each item based on their recall of the past month and the degree to which they perceived

events as being stressful on a 5 point scale (never –almost never – sometimes – fairly often – very often). Four positively stated items are the reverse scored and then all scores are summed for an overall perceived stress score with higher score representing more perceived stress. A validated Dutch version is available.

### **Diabetes Distress: PAID**

*The Problem Areas in Diabetes (PAID)* questionnaire is a 20-item measure of psychosocial adjustment to diabetes (18). Each of the 20 items represents a unique area of diabetes-related distress which are rated on a 5 point Likert scale (range = 0-4). These individual items are then added together and multiplied by 1.25 to transform the raw score into a 0-100 scale with higher scores representing increased emotional distress. The PAID was developed for routine clinical usage in both T1DM and T2DM. The PAID has been validated in Dutch (19).

### **Diabetes Self-Management: SDSCA and DSMQ-R**

*The Summary of Diabetes Self-Care Activities (SDSCA)* .The SDSCA is a short questionnaire that covers basic aspects of diabetes self-care in regards to general diet, specific diet, exercise, blood-glucose testing, foot care, and smoking (20). The core questionnaire consists of 11 questions but it can be expanded and adapted to specific needs using the additional self-care items published with the original instrument. The core set of questions has been validated in Dutch.

*The Diabetes Self-Management Questionnaire-Revised (DSMQ-R)* questionnaire is a revision of the original Diabetes Self-Management Questionnaire and contains 20- items that asks the patient about their self-management based on the previous days (21). These items can be grouped into four subscales (glucose management, dietary control, physical activity, and physician contact) from which an overall sum score for 'diabetes self-management' can be calculated. All subscales as well as the overall sum score have shown to be highly correlated with levels of HbA1c. Additionally, the revised version has an additional 7-item subscale containing questions specific to insulin usage intended for patients using insulin.

### **Relationship between well-being/distress and glycemc control**

To assess the relationship between well-being/distress and glycemc control, a (stepwise) hierarchical regression analysis will be performed, with HbA1c during self-quarantine as dependent variable and demographics (age, gender, education), diabetes/treatment related variables (type of diabetes, medication, previous HbA1c), well-being (WHO-5)

stress (PSS) and distress (PAID) as independent variables.

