The current study aims to assess the impact of self-quarantine on glycemetic control in patients with type 1 and type 2 diabetes. In addition, this study describes diabetes self-management, well-being and distress in Dutch patients with type 1 and type 2 diabetes, during a nationwide period of self-quarantine.

It is hypothesized that experiencing this period of nationwide quarantine influences glycemetic control and that patients reporting severe distress or low well-being experience more

problems in regard to diabetes self-management and maintaining glyceimic control than those without psychological distress or low well-being (13).

Research hypotheses:

H1: Experiencing self-quarantine impacts glyceimic control and glucose variability

H2: a) Experiencing high levels of distress is related to (poorer) glyceimic control

H2: b) Experiencing low levels of well-being is related to (poorer) glyceimic control

H3: a) Experiencing high levels of distress is related to suboptimal diabetes self-management

H3: b) Experiencing low levels of well-being is related to suboptimal diabetes self-management

H4: Experiencing self-quarantine impacts HbA1c, glucose variability, well-being, distress and self-management more in patients with type 1 than in patients with type 2 diabetes

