### 4.4. Sample size calculation

Patients with type 1 and type 2 diabetes mellitus are eligible for participation. HbA1c is the primary outcome parameter. Blood for HbA1c will be collected at home by a fingerprick and send to the LUMC. This is a method to obtain insight in glycemc control that many patients perform, and prefer, in clinical practice as it saves them a visit to the hospital. The clinical laboratory in the LUMC is set up to analyse these samples. But this method, which is appropriate in the context of social distancing and limiting hospital visits during this COVID-19 outbreak, also has some consequences regarding the number of patients that need to be approached. From clinical practice we know that not all patients carry out the blood sampling in an appropriate way, despite clear instructions. Also the duration in the postal service renders some samples not suitable for analysis. In this COVID-19 period the postal service

may take longer than normal. Based on our experience from clinical practice and the current COVID-19 situation we estimate that 20% of samples cannot be analysed for HbA1c. The aim is to detect a difference in HbA1c of 4.0 mmol/mol (standard deviation 11 mmol/mol) in comparison to the HbA1c prior to the period of quarantine, which is considered to be clinically relevant in our population of patients with often well regulated diabetes. For an alpha error of 0.05 and a power of 90%, the minimum sample needed is 159 patients per patient group (type 1 and type 2 diabetes). Taking in consideration an estimated response rate of 35% and an estimated proportion of 20% of HbA1c missing measurements as a result of logistical, practical or technical problems, 568 patients per patient group (type 1 and type 2 diabetes) will be invited to participate. This is a total of 1136 patients. The numbers of participants mentioned above are much higher than the number that is minimally needed (15 per variable) to calculate the hierarchical regression analyses (see statistical analyses) on secondary outcomes.

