### **Relationship between well-being/distress and diabetes self-management**

To assess the relationship between well-being/distress and self-management, five separate (stepwise) hierarchical regression analyses will be performed, with the total DSMQ-R self-management score, and four (DSMQ-R) diabetes self-management subscale scores (glucose management, dietary control, physical activity, physician contact) as five separate dependent variables. Independent variables are: demographics (age, gender, education) and diabetes/treatment related variables (type of diabetes, medication), well-being, stress (PSS) and distress (PAID).

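### Well-being and distress are separate hypotheses, but WHO-5, PSS and PAID enter the same (stepwise) models, so each scale's test depends on selection, on entry order or on the other two scales

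*Protocol*

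**What the plan says.** Section 1 of the protocol splits H2 and H3 into a distress part (a) and a well-being part (b), each worded as a plain association; the well-being part of H2 reads "H2: b) Experiencing low levels of well-being is related to (poorer) glyceimic control". Section 2 likewise lists well-being and distress as two separate secondary objectives in relation to glycaemic control.

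Section 10.2 gives the analyses. For H2, "a (stepwise) hierarchical regression analysis will be performed, with HbA1c during self-quarantine as dependent variable". The predictors are demographics, then diabetes and treatment variables including the previous HbA1c, then WHO-5, PSS and PAID. For H3, "five separate (stepwise) hierarchical regression analyses will be performed", one for the DSMQ-R total and one for each of four subscales, each again with all three psychological scales.

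On overlap, the WHO-5 paragraph of Section 10.2 states: "The WHO-5 has been found to correlate moderately to strongly with diabetes specific measures of distress and depression". It gives no coefficient and does not mention the PSS.

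The protocol does not say what the bracketed word stepwise means, whether the three scales form one block or several, or in what order they enter. Section 4.4 supports the regressions only by a rule of 15 patients per variable.

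**The concern.** H2a and H2b (and H3a and H3b) ask whether distress, and separately whether well-being, is related to the outcome. A model that holds all three scales answers something else: whether one scale adds to the other two. When scales overlap, these questions can have different answers.

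The word stepwise adds a second problem. If the software chooses which scales stay, the ordinary p-values and confidence intervals of the retained scales ignore that choice, and a scale that is truly related can be removed because a correlated one entered first. The report could then say that well-being, or distress, is not related to HbA1c or self-management when it was only displaced.

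**Working it through.** **Inputs from the protocol (Section 4.4).** "For an alpha error of 0.05 and a power of 90%, the minimum sample needed is 159 patients per patient group"; the aim is to "detect a difference in HbA1c of 4.0 mmol/mol (standard deviation 11 mmol/mol"); the response rate is 35%, with an "estimated proportion of 20% of HbA1c missing measurements".

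**The plan's own figures reproduce.** The two-sided two-sample formula gives 2 × (1.960 + 1.282)² × 11² / 4² = 158.9, so 159 per group. Invitations are 159 / (0.35 × 0.80) = 567.9, so 568 per group and 1136 in total. Expected for H2 are 2 × 159 = 318 patients with a usable HbA1c, before any loss for a missing earlier HbA1c. Expected for H3 are up to 1136 × 0.35 ≈ 398 responders. The 15-per-variable rule needs 9 × 15 = 135 for the nine named predictors of the H2 model, so it is met. It does not address overlap between predictors.

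**Assumptions, not in the protocol.** The three scales are scored in the same direction and correlate equally, at r = 0.4 to 0.7. For PSS this overlap is purely assumed. Each scale has a correlation of 0.20 with the outcome after covariates (shared signal). The two-sided level is 0.05.

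**Formulas.** Write c for the scale–outcome correlation.
- Own model: noncentrality = c√n / √(1 − c²) = 0.20 × 17.83 / 0.980 = 3.64, so power is 95%.
- Joint model: coefficient b = c / (1 + 2r); VIF = 1 / (1 − 2r²/(1 + r)); R² = 3bc; noncentrality = b√(n/VIF) / √(1 − R²).
- Example at r = 0.5: b = 0.10, VIF = 1.5, R² = 0.06, noncentrality = 0.10 × √212 / √0.94 = 1.50, so power is 32%.

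| r | VIF | Own model | Joint model, formula | Joint model, simulation | Kept by forward selection |
|---|---|---|---|---|---|
| 0.4 | 1.3 | 95% | 44% | 44% | 55% |
| 0.5 | 1.5 | 95% | 32% | 31% | 45% |
| 0.6 | 1.8 | 95% | 24% | 24% | 40% |
| 0.7 | 2.4 | 95% | 17% | 16% | 34% |

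Simulations used 1000 runs per cell; forward selection entered a scale at p < 0.05. With scale–outcome correlations of 0.15 to 0.25, joint power per scale ranges from about 10% to 66%. At n = 398 (H3) the pattern is the same: 98% in the own model (noncentrality 0.20 × 19.95 / 0.980 = 4.07), against 52%, 39%, 28% and 20% jointly by the formula above.

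**If stepwise means selection.** A given related scale is dropped in about 45% to 66% of runs. With no association at all, at least one scale is retained in about 11% to 12% of runs.

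**If it means blocks.** The result depends on the order:
- WHO-5 directly after the covariates, as the text lists it: its entry test is the own-model test, with 95% power. The PSS and PAID block is then tested net of WHO-5, with power falling from 79% (r = 0.4) to 35% (r = 0.7).
- PSS and PAID first: that block has 95% to 98% power. WHO-5 is then tested net of both, which is the joint-model column.
- All three in one block: the block test keeps 94% to 98% power but cannot tell distress from well-being.

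**If only PAID carries signal (0.20).** The joint model keeps 83% power for PAID at r = 0.5 and 66% at r = 0.7, and flags the other two in about 4% to 5% of runs.

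**The case against.** The strongest case for the plan has four parts.

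- **Each scale is still testable.** A reader might infer that the hypotheses cannot be tested separately, or that every reading of the method fails. The documents do not support that. With VIFs of about 1.3 to 2.4 at n = 318, each conditional effect is estimable. In the listed order, WHO-5 would be tested without any loss. This stands, but the protocol does not say that the list is the entry order, and in that order distress is still tested net of WHO-5.
- **The overlap is only partly documented.** A reader might take the protocol to say that all three scales overlap. It covers WHO-5 with diabetes-specific distress, which is what PAID measures; overlap involving PSS is an assumption. This stands.
- **The loss is not certain.** A reader might infer that real associations are likely to be lost. That depends on a shared signal. If one scale alone matters the loss is smaller, and the joint model then avoids crediting the others. This stands, so the size is conditional.
- **Mutual adjustment is legitimate and block detail can wait for the SAP.** True of block order as such, and mutual adjustment is a fair secondary question. But the protocol itself names a stepwise method and one shared predictor list for hypotheses that it words as separate associations. That is a stated choice, not an omission.

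**Conclusion.** The point holds in a limited form. The stated method does not reliably answer H2a, H2b, H3a and H3b as worded. Under data-driven selection, inference on the retained scales is invalid and a related scale can be dropped. Under block entry, the answer is either mutually adjusted or dependent on an unstated order.

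Under a shared signal (adjusted correlation 0.20 for each scale, inter-scale r of 0.4 to 0.7, n = 318), power per scale falls from about 95% to between 44% and 16%. It stays at 83% (r = 0.5) or 66% (r = 0.7) if only PAID matters. These figures rest on correlations that the protocol does not give. The case for changing the plan rests on the mismatch between hypothesis and model, and does not need any one of them. The analyses are secondary; the primary HbA1c comparison is not affected. This should be corrected before analysis.

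**What to change.** 1. Delete the word stepwise in both regression paragraphs of Section 10.2 and state that no predictor is selected by the data.
2. Test H2a, H2b, H3a and H3b with one model per scale: the planned demographic and diabetes/treatment block plus WHO-5 alone, PSS alone or PAID alone.
3. Since PSS and PAID both bear on distress, add a simple multiplicity rule for the pair, for example Holm. Even at 0.025, an own-model test under the assumptions above keeps about 92% power (3.64 − 2.24 = 1.40).
4. Keep the three-scale model, in a stated block order, as the supportive analysis of independent contribution.

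The cost is wording and a few more regressions on data that are collected anyway, with more coefficients to report. There is one real downside: a single-scale model can show a borrowed association. If only PAID has an effect of 0.20, WHO-5 has a marginal correlation of 0.5 × 0.20 = 0.10 to 0.7 × 0.20 = 0.14. At n = 318 it would then be significant alone in about 43% to 71% of studies. The joint model is there to reveal this, so both should be reported side by side. Which DSMQ-R score should decide H3 is a separate matter and is not needed for this change.

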### **Relationship between well-being/distress and diabetes self-management**

To assess the relationship between well-being/distress and self-management, five separate (stepwise) hierarchical regression analyses will be performed, with the total DSMQ-R self-management score, and four (DSMQ-R) diabetes self-management subscale scores (glucose management, dietary control, physical activity, physician contact) as five separate dependent variables. Independent variables are: demographics (age, gender, education) and diabetes/treatment related variables (type of diabetes, medication), well-being, stress (PSS) and distress (PAID).

### **10.3. Other study parameters**

NA

### **10.4. Interim analysis (if applicable)**

NA. This is a observational cross-sectional study.

## **11. ETHICAL CONSIDERATIONS**

### **11.1. Regulation statement**

The study will be conducted according to the principles of the 'declaration of Helsinki' (as amended by the 64th WMA General Assembly, Fortaleza, Brazil, October 2013) and in accordance with the Medical Research Involving Human Subjects Act (WMO).

### **11.2. Recruitment and consent**

Patients with type 1 and type 2 diabetes that are currently in care at the diabetes outpatient clinic will be sent a letter with study information and informed consent forms. Within several days after receiving the letter, patients will be contacted by phone by a member of the study team and invited to participate in the study as well as given the opportunity to ask questions. If patients are willing to participate they will be asked to sign the informed consent form and send it back to the LUMC by post. Once informed consent is provided, patients will be sent an envelope with a lancet, small tube and instructions to collect blood with a fingerprick. They will be asked to fill the tube that is in the envelope with several drops of blood until the mark on the tube is reached and send the envelope (special envelope for medical samples) back to the LUMC. At the LUMC the HbA1c will be measured by the clinical chemistry lab.

If patients are using a continuous or flash glucose monitor, data will be collected according to standard clinical practice and will be covering the last non-quarantine week and the quarantine period.

Additionally, patients will receive a link in their e-mail to a set of online questionnaires, containing the DSMQ-R, SDSCA, PSS, PAID and WHO-5, along with questions about level of education, medication use, social situation, employment, impact of self-quarantine on daily routines.

The HbA1c measurement and questionnaire will be performed once at the predicted end of the nationwide quarantine phase as a result of the COVID-19 outbreak.

### **11.3. Objection by minors or incapacitated subjects (if applicable)**

NA. Minors and incapacitated subjects are not eligible to participate.

### **11.4. Benefits and risks assessment, group relatedness**

The risks associated with participation in this study are limited. The primary potential foreseeable risk associated with participation in this study is negative feelings resulting from

the increased attention to the patient's illness and distress by filling out the questionnaires. Additionally, there is a burden of time for the patient for performing the fingerprick and filling out the questionnaires, however, this time is limited and the measurement is being performed only once. Performing the fingerprick may be another foreseeable risk, however, for most patients performing the fingerprick for measurement of blood glucose values is already part of their regular daily routine.

#### **11.5. Compensation for injury**

The sponsor/investigator has a liability insurance which is in accordance with article 7 of the WMO. The sponsor (also) has an insurance which is in accordance with the legal requirements in the Netherlands (Article 7 WMO). This insurance provides cover for damage to research subjects through injury or death caused by the study.

The insurance applies to the damage that becomes apparent during the study or within 4 years after the end of the study.

#### **11.6. Incentives (if applicable)**

Not applicable

## 12. ADMINISTRATIVE ASPECTS, MONITORING AND PUBLICATION

### 12.1. Handling and storage of data and documents

- All data will be handled confidentially and will be coded, according to the EU General Data Protection Regulation and Dutch Act on Implementation of the General Data Protection Regulation (AVG/UAVG). All data will be preserved for 15 years. A secure datasafe folder is used for all output and storage of all data. Only the researchers have access to this folder.
- Consent forms will be stored securely in a locked cabinet at the at the Leiden University Medical Center by the researchers. After giving consent, each patient will be provided with an unique study code. This unique study code contains no traceable data, such as birth date or names. This will be generated by a secured online database (CASTOR). CASTOR will be used to gather questionnaire data. No traceable data is stored in CASTOR. Access to CASTOR is restricted to only the researchers conducting the study. Two factor authorization is used to enter the database. After filling out the questionnaires, the export of the coded data is stored by the researcher in the datasafe. A secured list with restricted access (HIX eigen lijsten) will be used to enable coupling of the patient ID to the CASTOR study code, to ensure that HbA1c measurements can be matched to the questionnaire outcomes. Only the researchers of this study will have access to this list. The management of the key HIX and study ID is the responsibility of the PI. In the analysis phase of the study, the researchers do not have access to this key file.
- Patients' continuous or flash glucose measurements (FSL) will be collected according to standard clinical practice. They will be stored by study ID in the datasafe with access restricted to the researchers.
- HbA1c measurements will be done by the clinical laboratory of the LUMC and data will be stored in the electronic health dossier (HIX) using the patient ID. The blood sample is destroyed by the clinical laboratory immediately after use.

### 12.2. Monitoring and Quality Assurance

Monitoring will be executed by (internal) monitors of the LUMC according to the monitoring plan.

**12.3. Amendments**

Amendments are changes made to the research after a favourable opinion by the accredited METC has been given. All amendments will be notified to the METC that gave a favourable opinion. Non-substantial amendments will not be notified to the accredited METC and the competent authority, but will be recorded and filed by the sponsor.

**12.4. Annual progress report**

N.A.

**12.5. Temporary halt and (prematurely) end of study report**

The investigator/sponsor will notify the accredited METC of the end of the study within a period of 8 weeks. The end of the study is defined as 'completion of the report on primary and secondary outcomes'.

The sponsor will notify the METC immediately of a temporary halt of the study, including the reason of such an action.

In case the study is ended prematurely, the sponsor will notify the accredited METC within 15 days, including the reasons for the premature termination.

Within one year after the end of the study, the investigator/sponsor will submit a final study report with the results of the study, including any publications/abstracts of the study, to the accredited METC.

**12.6. Public disclosure and publication policy**

Results will be presented at national and international (diabetes) conferences, and published in peer reviewed (inter)national journals.

